### 11.3.2 Safety evaluation for moving from Part A to Part B

In addition to monitoring participant safety throughout the study period, the HVTN 115 PSRT will review all cumulative safety data available from groups 1 through 4 up to and including the 2-week visit after the third vaccination. Based on the assessment of this safety data, the HVTN 115 PSRT will make a decision regarding the appropriateness of moving to Part B from a safety perspective. The HVTN SMB may perform an additional unblinded review of this safety data to make the final determination based on safety for proceeding to part B.

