**Table 3-1 Schema**

Study arm	N	Month 0 (Day 0)	Month 2 (Day 56)	Month 4 (Day 112)	Month 8 (Day 224)	Month 12 (Day 364)
Part A						
Group 1	12	20 mcg CH505TF	20 mcg CH505TF	20 mcg CH505TF	20 mcg CH505TF	20 mcg CH505TF
Group 2	12	100 mcg CH505TF	100 mcg CH505TF	100 mcg CH505TF	100 mcg CH505TF	100 mcg CH505TF
Group 3	12	400 mcg CH505TF	400 mcg CH505TF	400 mcg CH505TF	400 mcg CH505TF	400 mcg CH505TF
Group 4	6	placebo	placebo	placebo	Placebo	placebo
Total Part A		42 (36/6)				
Study arm	N	Month 0 (Day 0)	Month 2 (Day 56)	Month 4 (Day 112)	Month 8 (Day 224)	Month 12 (Day 364)
Part B						
Group 5	20	TBD mcg CH505TF + placebo	TBD mcg CH505w53 + placebo	TBD mcg CH505w78 + placebo	TBD mcg CH505w100 + placebo	TBD mcg CH505w100 + placebo
Group 6	20	TBD mcg CH505TF + 4 mg DNA Mosaic-Tre	TBD mcg CH505w53 + 4 mg DNA Mosaic-Tre	TBD mcg CH505w78 + 4 mg DNA Mosaic-Tre	TBD mcg CH505w100 + 4 mg DNA Mosaic-Tre	TBD mcg CH505w100 + 4 mg DNA Mosaic-Tre
Group 7	20	TBD mcg CH505TF + placebo	TBD mcg CH505TF, w53 + placebo	TBD mcg CH505TF, w53, w78 + placebo	TBD mcg CH505w53, w78, w100 + placebo	TBD mcg CH505w78, w100 + placebo
Group 8	20	TBD mcg CH505TF + 4 mg DNA Mosaic-Tre	TBD mcg CH505TF, w53 + 4 mg DNA Mosaic-Tre	TBD mcg CH505TF, w53, w78 + 4 mg DNA Mosaic-Tre	TBD mcg CH505w53, w78, w100 + 4 mg DNA Mosaic-Tre	TBD mcg CH505w78, w100 + 4 mg DNA Mosaic-Tre
Group 9	10	placebo + placebo	placebo + placebo	placebo + placebo	placebo + placebo	placebo + placebo
Total Part B		90 (80/10)				
Total Part A + Part B		132 (116/16)				

Safety data and immune responses after Month 4 in Part A will inform the protein dose for Part B.

GLA-SE will be admixed with all proteins. The total dose of GLA-SE will be 10 mcg at all timepoints. The total volume for protein plus adjuvant for injection is 1 mL, mixed 1:1 by volume.

If the dose of each protein in Groups 5 and 6 is 20 mcg, the total dose of each protein in Groups 7 and 8 will also be 20 mcg. If the dose of each protein in Groups 5 and 6 is 100 mcg or 400 mcg, the dose of each protein in Groups 7 and 8 will be 100 mcg.

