## 6.3 Blinding

Participants and site staff (except for site pharmacists) will be blinded as to participant treatment arm/group assignments (eg, vaccine or control). Study product assignments are accessible to those HVTN CRS pharmacists, DAIDS protocol pharmacists and contract monitors, and SDMC staff who are required to know this information in order to ensure proper trial conduct. Any discussion of study product assignment between pharmacy staff and any other HVTN CRS staff is prohibited. The HVTN SMB members also are unblinded to treatment assignment in order to conduct review of trial safety.

When a participant leaves the trial prior to study completion, the participant will be told he or she must wait until all participants are unblinded to learn his or her treatment assignment.

Emergency unblinding decisions will be made by the site investigator. If time permits, the HVTN 115 PSRT should be consulted before emergency unblinding occurs.

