#### 6.4.5.1 Safety

During the course of the trial, unblinded analyses of safety data will be prepared approximately every 4 months for review by the SMB. Ad hoc safety reports may also be prepared for SMB review at the request of the HVTN 115 PSRT. The HVTN leadership must approve any other requests for unblinded safety data prior to the end of the scheduled follow-up visits.

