If the PSRT or sponsor believes unblinding of the site PI to treatment assignment will assist with the clinical management of the SAE, the PSRT will consult the independent HVTN SMB for a recommendation. In the event the HVTN SMB determines that unblinding is indicated, the SMB will inform the site physician of the participant's treatment assignment in such a manner as to maintain the study blind of the PSRT and study team. For additional impact and management of SAEs on the study, refer to Section 11.4.

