**Table 11-1 AE notification and safety pause/AE review rules**

Event and relationship to study products	Severity	HVTN CRS action a	HVTN Core action
SAE, related	Grade 5 or Grade 4	Phone immediately, email and submit forms immediately	Immediate pause
SAE, not related	Grade 5	Phone immediately, email and submit forms immediately	Immediate HVTN 115 PSRT notification
SAE, related	Grade 3	Email and submit forms immediately	Prompt HVTN 115 PSRT AE review to consider pause
AE b , related	Grade 4 or 3	Email and submit forms immediately	Prompt HVTN 115 PSRT AE review to consider pause

a Phone numbers and email addresses are found on the Protocol home page on the HVTN Members' site (<https://members.hvtn.org/protocols/hvtn115>).

b Does not include subjective reactogenicity symptoms (injection site pain, tenderness, fatigue/malaise, myalgia, arthralgia, chills, headache, nausea).

For all safety pauses, HVTN Core notifies the HVTN 115 PSRT, HVTN Regulatory Affairs, DAIDS Pharmaceutical Affairs Branch (PAB), DAIDS Regulatory Affairs Branch (RAB), DAIDS Safety and Pharmacovigilance Team (SPT), and participating HVTN CRSs. When an immediate safety pause is triggered, HVTN Core notifies the SMB.

Once a trial is paused, the HVTN 115 PSRT reviews safety data and decides whether the pause can be lifted or permanent discontinuation of vaccination is appropriate, consulting the SMB if necessary. HVTN Core notifies the participating HVTN CRSSs, HVTN Regulatory Affairs, DAIDS PAB, DAIDS RAB, and DAIDS SPT of the decision regarding resumption or discontinuation of study vaccinations. Based on the HVTN 115 PSRT assessment, DAIDS RAB notifies the FDA as needed.

If an immediate HVTN 115 PSRT notification or prompt HVTN 115 PSRT AE review is triggered, HVTN Core notifies the HVTN 115 PSRT as soon as possible during working hours (US Pacific Time)—or, if the information was received during off hours, by the morning of the next work day. If a prompt HVTN 115 PSRT AE review cannot be completed within 72 hours of notification (excluding weekends and US federal holidays), an automatic safety pause occurs.

The HVTN requires that each CRS submit to its IRB/EC and any applicable RE protocol-related safety information (such as IND safety reports, notification of vaccine holds due to the pause rules, and notification of other unplanned safety pauses). CRSSs must also follow all applicable RE reporting requirements.

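### Opening Part B does not require a by-dose safety review of Part A through day 126: section 11.3.2 leaves the decision with a blinded PSRT and makes the unblinded SMB review optional

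*Combined protocol and SAP*

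**What the plan says.** **Safety is an input to the Part B dose.** The notes to Table 3-1 state: "Safety data and immune responses after Month 4 in Part A will inform the protein dose for Part B". Sections 4.5, 4.5.1 and 4.9.1 say the same, and comparing the safety of the doses is the first primary objective of Part A (section 5.1).

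**Who decides.** Under section 11.3.2, after reviewing Groups 1-4 through the visit two weeks after vaccination 3, "the HVTN 115 PSRT will make a decision regarding the appropriateness of moving to Part B from a safety perspective". The next sentence adds that "The HVTN SMB may perform an additional unblinded review of this safety data to make the final determination".

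**Who is blinded.** Section 6.3 does not list the PSRT among those with access to assignments. It does list the SMB: "The HVTN SMB members also are unblinded to treatment assignment in order to conduct review of trial safety". Section 11.2.3 confirms the PSRT's status indirectly: if a site physician has to be unblinded, this is done "in such a manner as to maintain the study blind of the PSRT and study team".

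**Unblinded safety review outside 11.3.2.** Section 6.4.5.1 provides that "unblinded analyses of safety data will be prepared approximately every 4 months for review by the SMB", and section 11.1.2 repeats the interval. Both sections let the PSRT ask for an extra SMB review. For anything else, "The HVTN leadership must approve any other requests for unblinded safety data prior to the end of the scheduled follow-up visits".

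**Immunogenicity.** Section 6.4.5.2 allows an analysis by treatment assignment once everyone has passed the primary immunogenicity visit (day 126 in Part A, section 10.3) and data are in for at least 80%. Recipients include the protocol chairs and DAIDS. The protocol chair, the cochair and a DAIDS medical officer representative also sit on the PSRT (section 11.1.1).

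**The concern.** Part A is a dose-ranging study whose results set the protein doses for the 80 Part B vaccinees. To judge safety by dose, someone has to see it by dose. At this decision point the body required to act sees Groups 1-4 as one mixture of 42 people, and the body able to separate the arms is only permitted to act.

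All Part A groups enroll at the same time (section 11.3.1), so order of entry tells a blinded reader nothing about dose. The information is also uneven. Immune response by arm may be released on the day-126 data, while no safety comparison by arm on those data is required. If one dose were less well tolerated than the others, the plan as written would not ensure that anyone saw this before Part B opened.

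**Working it through.** **1. The plan's own sensitivity figures.** There is no stated figure for the Part A to Part B decision itself, so I checked the Part A safety figures in section 6.1.1.
- Event rate giving a 90% chance of at least one event: 1 − 0.1^(1/n). For n = 12 this is 17.46% (stated 17.5%); for n = 36 it is 6.20% (stated 6.2%).
- Score upper 95% bound for 0/n: 24.25% for n = 12 (stated 24.2%) and 9.64% for n = 36 (stated 9.6%).

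These reproduce. The n = 12 figures describe a reader who sees one arm.

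**2. What a blinded reader sees.** Inputs from Table 3-1: 12 per dose arm, three dose arms, 6 placebo, 42 in total. If x events all fall in one dose arm, the pooled rate is x/42 instead of x/12, a dilution of 42/12 = 3.5. The counts below are assumptions; intervals are 95% score intervals.

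| Events, all in one arm | By arm, x/12 | Pooled, x/42 |
|---|---|---|
| 2 | 16.7% (4.7 to 44.8) | 4.8% (1.3 to 15.8) |
| 3 | 25.0% (8.9 to 53.2) | 7.1% (2.5 to 19.0) |
| 4 | 33.3% (13.8 to 60.9) | 9.5% (3.8 to 22.1) |
| 6 | 50.0% (25.4 to 74.6) | 14.3% (6.7 to 27.8) |

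With an assumed background, 25% in one arm and 2% elsewhere gives (12 × 0.25 + 30 × 0.02)/42 = 3.6/42 = 8.6%.

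**3. What the arm labels add.** With no dose effect, the chance that all x events fall in one named dose arm is C(12,x)/C(42,x). This equals the Fisher exact p for x/12 versus 0/30. For any one of the three dose arms, multiply by 3.
- x = 2: 66/861 = 0.077; any arm 0.230.
- x = 3: 220/11,480 = 0.019; any arm 0.057.
- x = 4: 495/111,930 = 0.0044; any arm 0.013.

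Two clustered events would settle little even unblinded. Four would be a clear pattern by arm, yet would look like a scattered 9.5% when pooled.

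**4. Timing.** Day 126 is 126/30.4375 = 4.14 months after a participant's own enrollment, so about one routine SMB review should fall before the decision. Nothing fixes its date. Taking the interval as exactly four months (121.75 days), the latest review could fall as early as day 126 − 121.75, about day 4, for the last person enrolled. That person would then have had one vaccination; the second is at day 56. Earlier enrollees would contribute more.

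**5. What is caught without arm labels.** Table 11-1 sends related Grade 4-5 SAEs to an immediate pause, and related Grade 3 SAEs and Grade 3-4 AEs to prompt PSRT review. Its footnote b removes subjective reactogenicity symptoms (pain, tenderness, fatigue, headache and similar) from the AE row, and Grade 1-2 events are not listed. These are the events that dilution affects.

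**The case against.** **By-arm review already exists.** A reader of 11.3.2 alone might infer that the only unblinded safety review is optional. The documents do not support that: sections 6.4.5.1 and 11.1.2 make SMB review by arm a standing requirement. The PSRT can also request more, HVTN leadership can approve other requests, and section 4.5 has the Part B dose information submitted to the FDA before Part B opens. This argument stands and limits the point to timing and linkage. It does not remove it: a routine review need not contain the post-vaccination-3 data, and a blinded team may have no reason to request one when the pooled picture looks unremarkable.

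**The PSRT does not pick the dose.** Section 11.3.2 gives it only the decision to proceed on safety grounds, and section 4.8.1 bases the dose on binding antibody data informed by memory B-cell data. A reader might infer that the dose will be chosen with immune response known by dose and safety not. The text permits that but does not prescribe it; no passage says who selects the dose or what safety data they see.

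**Serious toxicity would not be hidden.** This is correct for events covered by Table 11-1. Daily Core screening and weekly PSRT review (section 11.5) apply to individual events, and 11.3.2 sets no pooled-rate threshold. Section 4.9.1 also reports broadly similar safety across gp120 doses, although one cited study had fewer reactogenicity events at its lowest dose.

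**Safety pauses.** A reader might extend the point to section 11.4, where the PSRT decides whether to lift a pause, "consulting the SMB if necessary". The same section has the SMB notified of every immediate pause, and there is no contradiction to resolve. I make no point there.

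**Conclusion.** The point holds in a limited form. Before Part B opens, the plan does not require anyone to review Part A safety by dose arm on data through day 126, although it says that safety informs the Part B dose. The required decision-maker is blinded, the unblinded review at that point is optional, and the routine four-monthly SMB reviews are not linked to the decision and could precede the relevant data by up to about four months.

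The size is a 3.5-fold dilution of any event confined to one dose arm. This follows from the arm sizes; the example counts and rates are assumed. The practical effect is mainly on Grade 1-2 events and subjective reactogenicity, which is where tolerability by dose would be judged. The timing figure assumes an SMB interval of four months, which the protocol states only approximately. This is an inexpensive improvement to a decision procedure; it does not show that the plan leaves dose-level safety unmonitored.

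**What to change.** In section 11.3.2, change 'may perform' to 'will perform'. State that, before Part B opens, the SMB reviews Part A safety unblinded by dose arm, including all data through the day-126 visit, and gives the PSRT only its recommendation. By-arm figures should not pass to the PSRT, which stays blinded while Part A vaccinations continue at months 8 and 12. The current sentence gives the SMB the final determination if it acts, so the revised wording should say plainly how the recommendation and the PSRT decision fit together.

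The cost is one scheduled SMB review at a hold already planned, using a board and unblinded reports that already exist. Sample size, power and alpha do not change, and no change to section 11.4 is proposed.

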## 11.4 Safety pause and prompt PSRT AE review

When a trial is placed on safety pause, all enrollment and vaccination with the product related to the event that triggered the pause will be held until further notice. The AEs that will lead to a safety pause or prompt HVTN 115 PSRT AE review are summarized in Table 11-1. Vaccinations may be suspended for safety concerns other than those described in the table, or before pause rules are met, if, in the judgment of the HVTN 115 PSRT, participant safety may be threatened. Criteria for an individual participant's departure from the schedule of vaccinations are listed in Section 7.3.

**Table 11-1 AE notification and safety pause/AE review rules**

Event and relationship to study products	Severity	HVTN CRS action a	HVTN Core action
SAE, related	Grade 5 or Grade 4	Phone immediately, email and submit forms immediately	Immediate pause
SAE, not related	Grade 5	Phone immediately, email and submit forms immediately	Immediate HVTN 115 PSRT notification
SAE, related	Grade 3	Email and submit forms immediately	Prompt HVTN 115 PSRT AE review to consider pause
AE b , related	Grade 4 or 3	Email and submit forms immediately	Prompt HVTN 115 PSRT AE review to consider pause

a Phone numbers and email addresses are found on the Protocol home page on the HVTN Members' site (<https://members.hvtn.org/protocols/hvtn115>).

b Does not include subjective reactogenicity symptoms (injection site pain, tenderness, fatigue/malaise, myalgia, arthralgia, chills, headache, nausea).

For all safety pauses, HVTN Core notifies the HVTN 115 PSRT, HVTN Regulatory Affairs, DAIDS Pharmaceutical Affairs Branch (PAB), DAIDS Regulatory Affairs Branch (RAB), DAIDS Safety and Pharmacovigilance Team (SPT), and participating HVTN CRSs. When an immediate safety pause is triggered, HVTN Core notifies the SMB.

Once a trial is paused, the HVTN 115 PSRT reviews safety data and decides whether the pause can be lifted or permanent discontinuation of vaccination is appropriate, consulting the SMB if necessary. HVTN Core notifies the participating HVTN CRSSs, HVTN Regulatory Affairs, DAIDS PAB, DAIDS RAB, and DAIDS SPT of the decision regarding resumption or discontinuation of study vaccinations. Based on the HVTN 115 PSRT assessment, DAIDS RAB notifies the FDA as needed.

If an immediate HVTN 115 PSRT notification or prompt HVTN 115 PSRT AE review is triggered, HVTN Core notifies the HVTN 115 PSRT as soon as possible during working hours (US Pacific Time)—or, if the information was received during off hours, by the morning of the next work day. If a prompt HVTN 115 PSRT AE review cannot be completed within 72 hours of notification (excluding weekends and US federal holidays), an automatic safety pause occurs.

The HVTN requires that each CRS submit to its IRB/EC and any applicable RE protocol-related safety information (such as IND safety reports, notification of vaccine holds due to the pause rules, and notification of other unplanned safety pauses). CRSSs must also follow all applicable RE reporting requirements.

In addition, all other AEs are reviewed routinely by the HVTN 115 PSRT (see Section 11.5.2).

## **11.5 Review of cumulative safety data**

Routine safety review occurs at the start of enrollment and then throughout the study.

Reviews proceed from a standardized set of protocol-specific safety data reports. These reports are produced by the SDMC and include queries to the HVTN CRSSs. Events are tracked by internal reports until resolution.

### **11.5.1 Daily review**

Blinded daily safety reviews are routinely conducted by HVTN Core for events requiring expedited reporting to DAIDS, and events that meet safety pause criteria or prompt HVTN 115 PSRT AE review criteria.

### **11.5.2 Weekly review**

During the injection phase of the trial, the HVTN 115 PSRT reviews clinical safety reports on a weekly basis and conducts calls to review the data as appropriate. After the injections and the final 2-week safety visits are completed, less frequent reporting and safety reviews may be conducted at the discretion of the HVTN 115 PSRT. HVTN Core reviews reports of clinical and laboratory AEs. Events identified during the review that are considered questionable, inconsistent, or unexplained are referred to the HVTN CRS clinic coordinator for verification.

## **11.6 Study termination**

This study may be terminated early by the determination of the HVTN 115 PSRT, a pertinent national regulatory authority, NIH, FDA, Office for Human Research

Protections (OHRP), or vaccine developer(s). In addition, the conduct of this study at an individual HVTN CRS may be terminated by the determination of the IRB/EC and any applicable RE.

## 12 Protocol conduct

This protocol and all actions and activities connected with it will be conducted in compliance with the principles of GCP (ICHe6), and according to DAIDS and HVTN policies and procedures as specified in the *HVTN Manual of Operations*, DAIDS Clinical Research Policies and Standard Procedures Documents including procedures for the following:

- Protocol registration, activation, and implementation;
- Informed consent, screening, and enrollment;
- Study participant reimbursement;
- Clinical and safety assessments;
- Safety monitoring and reporting;
- Data collection, documentation, transfer, and storage;
- Participant confidentiality;
- Study follow-up and close-out;
- Unblinding of staff and participants;
- Quality control;
- Protocol monitoring and compliance;
- Advocacy and assistance to participants regarding negative social impacts associated with the vaccine trial;
- Risk reduction counseling;
- Specimen collection, processing, and analysis;
- Ancillary studies, and
- Destruction of specimens.

Any policies or procedures that vary from DAIDS and HVTN standards or require additional instructions (eg, instructions for randomization specific to this study) will be described in the HVTN 115 *Study Specific Procedures*.

### 12.1 Social impacts

Participants in this study risk experiencing discrimination or other personal problems, resulting from the study participation itself or from the development of VISp. The HVTN

CRS is obliged to provide advocacy for and assistance to participants regarding these negative social impacts associated with the vaccine trial. If HVTN CRS staff have questions regarding ways to assist a participant dealing with a social impact, a designated NIAID or HVTN Core representative can be contacted.

Social harms are tabulated by the SDMC and are subjected to descriptive analysis. The goal is to reduce their incidence and enhance the ability of study staff to mitigate them when possible.

Summary tables of social impact events will be generated weekly, and made available for review by the protocol chairs, protocol team leader, and the designated NIAID representative.

## **12.2 Compliance with NIH guidelines for research involving products containing recombinant or synthetic Nucleic Acid Molecules**

Because this study is evaluating products containing recombinant or synthetic DNA, it must comply with regulations set forth in the NIH's *Guidelines for Research Involving Recombinant or Synthetic Nucleic Acid Molecules* (April 2016). Information about the study must be submitted to site Institutional Biosafety Committees (IBCs). Investigators at each site are responsible for obtaining IBC approval per NIH guideline *section IV-B7-a-(1)*. IBC review and approval must be documented by the investigator and submitted as part of DAIDS initial protocol registration for this trial before participants are enrolled at the site. If this protocol is amended, investigators should follow the requirements of their IBC.

## **12.3 Emergency communication with study participants**

As in all clinical research, this study may generate a need to reach participants quickly to avoid imminent harm, or to report study findings that may otherwise concern their health or welfare.

When such communication is needed, the CRS will request that its IRB/EC and any applicable RE expedite review of the message. If this review cannot be completed in a timeframe consistent with the urgency of the required communication, the site should contact the participant first, and then notify the IRB/EC and any applicable RE of the matter as soon as possible.

